1.0 STUDY OBJECTIVE AND BACKGROUND

Study Objective:

The objectives of this study are to evaluate, in trigeminal nerve block procedures for painful trigeminal neuropathy adult patients between 18 and 80 years of age,

- 1. The efficacy of guanfacine in combination with lidocaine compared to lidocaine alone in extending the pain relief duration.
- 2. The safety and tolerability of a single dose of guanfacine in combination with lidocaine compared to lidocaine alone.

Background:

Painful trigeminal neuropathy is a severely painful condition affecting cranial nerve V (trigeminal nerve) that transmits sensation from the face. Painful trigeminal neuropathy affects one or more branches of the trigeminal nerve, most often the second (V2, maxillary) or third (V3, mandibular) division. The latest classification (ICHD-3) by the International Headache Society (IHS) distinguishes trigeminal nerve pain into trigeminal neuralgia and painful trigeminal neuropathy. Classical trigeminal neuralgia includes cases that develop idiopathically or secondary to neurovascular compression. Painful trigeminal neuropathy is caused by structural abnormalities or neural damage rather than vascular compression. Common causes of painful trigeminal neuropathy include multiple sclerosis, tumors, acute herpes zoster, post-chemotherapy neuritis, post-radiation therapy neuritis, and space occupying abnormalities. The pain associated with painful trigeminal neuropathy is highly variable in quality and intensity. Painful trigeminal neuropathy is characterized by continuous or near-continuous facial pain often described subjectively as burning, squeezing, electrical, or likened to pins and needles.

The current treatment strategy for trigeminal neuralgia and painful trigeminal neuropathy includes the use of neuropathic pain medications (carbamazepine, oxcarbazepine, gabapentin, lamotrigine) and interventional procedures ranging from conservative local blocks to more invasive ablative procedures.^{2–5} Traditionally, anticonvulsant and antidepressant medications are used to raise the threshold for neural signaling and reduce the severity of neuropathic pain sensed by the patient. Acute and chronic neuropathic pain treatment with these classes of medications is often insufficient, and opioids are added with the understanding of their accompanying risks and decreasing long-term benefits. Likewise, there are no supportive studies of chronic opioid use for functional improvement of trigeminal nerve pain. Medical management using neuropathic pain medications remains first line treatment for most patients, and progression to surgical or interventional management is not uncommon when standard medical therapy fails. 6,7 The decision to perform interventional or surgical procedures are based on many factors, including the patient's age, their overall health and ability to tolerate the procedure, the duration and intensity of pain and its impact on quality of life, and on patient preference. 8 Interventional procedures offered to patients with intractable trigeminal nerve pain often begin with diagnostic regional block with local anesthetic to ensure peripheral treatment of first-order neurons will adequately relieve the patient's pain. Further subsequent, standard treatments include repeat regional blocks with addition of adjunctive medications (i.e. steroids, clonidine, or botulinum toxin), or progression to trigeminal nerve ablation via radio-frequency or balloon compression, or radiotherapy.

Trigeminal nerve block using local anesthetic with or without adjuvants have been effective in relieving pain temporarily in some trigeminal neuralgia patients.^{8–12} 2% lidocaine perineural injection (2-4 ml) in combination with neuropathic pain medications has been shown to be safe and effective in reducing pain, lowering the frequency of pain attacks, and reported improvement in the quality of life in classical trigeminal neuralgia patients.¹³ High concentration (10% lidocaine) perineural injection with no adjuvant has been shown to be safe

and effective in reducing pain in certain trigeminal neuralgia patients.⁸ After these blocks, pain often returns to previous levels of severity. The potential for more durable benefit from interventional blocks is, therefore, an unmet medical need. Importantly, adjuvants in combination with lidocaine, such as clonidine or dexamethasone, or other steroids have previously been shown to extend the duration of the block in other regional anesthesia techniques.^{14,15} The proposed therapeutic approach is ultimately intended to generate durable relief of neuropathic pain without the potential side effects of steroids.

Alpha-2-adrenergic receptor function in managing pain

The alpha-2 adrenoreceptor has important roles in signaling within and between both the peripheral and central nervous systems. Stimulation of the alpha-2 adrenoreceptor suppresses calcium entry into the nerve terminal; it has been postulated that this dynamic is responsible for its inhibitory effect on secretion of neurotransmitters, leading to interruption of the propagation of pain signals. Both central and peripheral alpha-2 adrenoreceptors are proposed to mediate interruption of pain signaling by this mechanism. In humans, both the alpha 2A and 2B subtypes are expressed in the spinal cord and have been shown to be involved in antinociceptive activity. Alpha-2 adrenergic agonists mitigate postoperative neuropathic pain in rats.

Alpha-2 adrenergic agonists such as clonidine and dexmedetomidine have been successfully used as adjuvants to local anesthetics to extend by several hours, regional blocks used for surgical analgesia or acute and chronic pain treatment. ¹⁴ Clonidine (30 to 300 μ g) is a well-known adjuvant for extending and enhancing the effect of local anesthetics. ¹⁵ Dexmedetomidine dose-dependently (4.5 to 13.5 μ g) enhances the local anesthetic action of lidocaine in inferior alveolar nerve blocks (IANB). ²² Clonidine (75 μ g) with (10 ml) lidocaine, bupivacaine, and fentanyl has been used in trigeminal nerve block to manage pain in trigeminal neuralgia patients without significant adverse events. ²³

Guanfacine is the oldest alpha-2 adrenergic agonist in clinical use in this class.²⁴ Of the alpha-2 agonists, guanfacine has the lowest rate of sedation. 25 Guanfacine is currently approved in tablet form for the treatment of hypertension (1 to 2 mg) and Attention Deficit Hyperactivity Disorder (1 to 4 mg). Guanfacine is readily absorbed with around 80% oral bioavailability and has an elimination half-life of ~17 h with renal excretion accounting for ~50%. Guanfacine has been shown to have similar in vitro potency as clonidine to inhibit conduction in rat sciatic nerve fibers.²⁷ Intrathecal guanfacine has a similar antinociceptive effect as that of intrathecal clonidine in a goat model.²⁸ Guanfacine showed longer antinociceptive effect in comparison to clonidine (8 h vs. 5 h) due to slower elimination of guanfacine from spinal cord tissue. In a rat model, intrathecal guanfacine has shown antinociceptive effect for greater than 18 h (both 25 mcg and 50 mcg) in comparison to clonidine injection (50 mcg) which declined to baseline within 4 h.²⁹ This study also reported a lower rate of elimination of guanfacine from spinal cord tissue compared to clonidine. Highly concentrated guanfacine (75 mcg in 15 µl saline) solution administered through an intrathecal route has been shown to be nontoxic in the subarachnoid space, establishing the safe use of guanfacine for perineural blockade.³⁰ Guanfacine as studied in animals and used in humans has a safe risk profile, suggesting that repurposing it for other indications. Guanfacine has the potential to be developed as a safe, non-opioid, analgesic for acute and chronic debilitating pain. Guanfacine in combination with 1% lidocaine is expected to be safe and to provide an extended duration of pain relief in painful trigeminal neuropathy patients who are not able to obtain pain relief from standard neuropathic pain medication.

PheWAS data indicating the role of the alpha-2-adrenergic receptor in trigeminal nerve pain

BioVU is a large repository of de-identified DNA samples that Vanderbilt University Medical Center (VUMC) has cataloged for >10 years from what otherwise would have been excess, discarded patient blood samples collected during routine clinical testing. Biospecimens within BioVU are linked to corresponding longitudinal clinical and demographic data derived from the Synthetic Derivative, our de-identified database of EMRs. 31-33

Phenome-wide association studies (PheWAS) is a systematic and efficient approach to discover novel disease-variant associations and pleiotropy using BioVU, a centralized resource for investigating genotype-phenotype associations.³⁴ It is the comprehensive and diverse nature of the diagnostic information within EMRs that enables PheWAS. PheWAS not only replicates known genetic-phenotypic associations but also reveals new phenotypic associations with genetic variants, enhancing analyses of the genomic basis of human diseases and providing genetic support for drug discovery and drug repurposing efforts.^{35–38}

Using PheWAS data we were able to identify a potentially use of guanfacine in treating trigeminal nerve pain. Genetic data from BioVU show that patients with a variant alpha 2B subtype receptor also have an increased likelihood of being diagnosed with trigeminal nerve disorders.

2.0 STUDY DESIGN

Primary Hypothesis:

Due to its different but relevant mechanism of action, guanfacine will be an effective adjunct to lidocaine in trigeminal nerve block for the treatment of painful trigeminal neuropathy by enhancing and prolonging pain relief compared to lidocaine alone.

Endpoints

The following endpoints will be measured to evaluate the exploratory objectives of the study assessing guanfacine and lidocaine in combination compared to lidocaine alone, in pain management in the painful trigeminal neuropathy patient.

- Primary endpoint: time to return to baseline pain (VAS) measurement after treatment with guanfacine as adjuvant to 1% lidocaine compared to 1% lidocaine alone
- Safety endpoint: comparable side effect profile of combination product compared to lidocaine alone on relevant adverse event measures: sedation, local site reaction, confusion
- Secondary endpoint: pain intensity after treatment to be measured throughout the follow-up periods on a visual analog scale (VAS)
- Secondary endpoint: quality of life after treatment to be measured using PROMIS Global Health -10 SF during the follow-up periods
- Secondary endpoint: frequency of acute trigeminal nerve pain attacks during the follow-up periods
- Secondary endpoint: total amount of rescue medications (opioid and non-opioid analgesics) for pain management during the follow-up periods
- Secondary endpoint: time to first rescue medication during the follow-up periods

Experimental Design

The trial is designed as a single-center, randomized, double-blind, controlle, 2x2 crossover pilot study with two arms: study drug (guanfacine and lidocaine combination) and active control (lidocaine alone). The target sample size is 30 study drug vs. 30 active control.

Not all participants that are randomized and initiate the first arm of the trial will *necessarily* complete *both* arms of the crossover trial. Based on previous experience, initiating the first arm of the cross over trial in 40 participants should be sufficient reach the full sample size (30 study drug vs. 30 active control). The trial will be complete and enrollment will cease upon reaching the full proposed sample size (30 study drug vs. 30 active control).

Approximately 80 patients meeting preliminary enrollment criteria will be consented for screening with the goal of roughly half being eligible to randomize and begin participation in the trial.

Inclusion Criteria

- Adults between 18 and 80 years of age
- Ability to understand and read English
- History of painful trigeminal neuropathy with persistent background facial pain severity > 5/10 on VAS
- Experience pain with a score of greater than 5 on a 0-10 scale (VAS) in the previous 24 hours before procedural treatment and at the time of procedural treatment
- Eligible for trigeminal nerve block procedure and have not had a trigeminal nerve block procedure for pain management prior to enrollment in the current study
- Women of childbearing potential to provide agreement to use 2 forms of birth control while in the study
- Able to provide informed consent

Exclusion Criteria

- Presence of a significant structural lesion (e.g., tumor) as the cause of pain as shown in at least one neuroimaging study.
- Current diagnosis of fibromyalgia, temporomandibular disorders (TMD), odontogenic pain or other orofacial pain deemed unrelated to the trigeminal nerve as the origin.
- Allergy or any other hypersensitivity reactions to guanfacine or lidocaine or local anesthetic of the amide type, or to both iodinated contrast and gadolinium contrast.
- Females who are pregnant or breastfeeding and/or plan to become pregnant or to breastfeed during study participation.
- Inappropriately positive illicit drug test.
- Participation in another investigational drug study within 30 days before randomization.
- Inability to understand the requirements of the study, inability to abide by the study restrictions, inability to fill out the questionnaires, or inability to return for the required treatments.
- Any clinically significant medical or surgical condition that in the investigator's opinion could interfere with the administration of study drug, interpretation of study results, or compromise the safety or well-being of the subject (i.e. infection, unable to stop anticoagulants).
- No reliable access to telephone service to allow for contact with study personnel.

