5.0 STUDY PROCEDURE

The study is a single center, randomized, double-blind, 2 x 2 crossover pilot study with two arms; study drug (guanfacine and lidocaine combination) and active control (lidocaine alone). Adult participants between 18 and 80 years of age who have been diagnosed with painful trigeminal neuropathy will be consented for the study. The study includes three visits; an initial visit for evaluation, consent, and baseline surveys followed by two procedural visits. After each procedural visit data will be collected for 14 days. Participants will be randomized in permuted pairs (to ensure balance after every second enrollment) to receive either study drug (guanfacine and lidocaine combination) or active control (lidocaine alone) for the first nerve block procedure. Following the first procedural visit and 14-day follow up period, the study team will assess inclusion and exclusion criteria and (if eligible) schedule the second procedural visit.

Assessment	Study Visit 1: Consent and screening (Day -15 to 0)	Study Visit 2: Procedure 1 (Day 1)	Follow-up period 1 (Day 2-14)	Study Visit 3: Procedure 2 (≥15 days after procedure 1)	Follow-up period 2 (14 days after procedure 2)
		Administrative P	rocedures		
Eligibility Review	X	X		X	
Informed Consent	X				
Demographics	X				
Pain History	X				
Baseline Pain	X	X	X	X	X
Medical History	X				
Concomitant Medications	X	X		X	
Surgical/ Past Treatments History	X				
Verbal Pregnancy Screen	X				
PROMIS Global 10- SF	X	X	X \$	X	X \$
Pain Interference	X	X		X	
Pain Intensity (VAS Score)	X	X #	X %	X #	X
Frequency of Attacks	X	X	X \$	X	X \$
Rescue Medications		X %	X %	X %	X
Randomization	X				
	Cl	inical Procedures/	Assessments		•
Physical Exam (general)	X	X		X	
Physical Exam (pain)	X				
Vitals (HR, RR, Temp, BP)	X	X		X	
Height/ Weight	X				
12-Lead ECG ^	X				
Continuous ECG monitoring		X		X	
Nerve Block Administration		X		X *	
Imaging MRI/ CT report +	X				
Adverse Events		X	X	X	X
		Laboratory Pro	cedures		
Urine Pregnancy Test		X		X	
Urine Drug Screen	X				

^{#:} Collected every 30 minutes for 8 hours by text message (REDCap) or patient diary

^{%:} Collected daily for up to 28 days by text message (REDCap) or patient diary

Collected weekly for up to 4 weeks by study nurse phone call

If pain score >5

^{+:} Review recent imagining, if not available then order as standard of care
^: Order 12-lead ECG as standard of care if one not available within 2 months of screening visit

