6.0 RISKS

During the consent process, study personnel will address potential discomfort and risks associated with the protocol. These will be included in the consent form.

Based on the known common side effects of the study drugs and the trigeminal block procedure, the following risk associated with participation in the study are perceived as low:

- Bradycardia
- Hypotension
- Dry Mouth
- Sedation
- Dizziness
- Headache
- Bruising, redness, itching, or swelling at the site of injection
- Intravascular injection resulting in seizure or stroke
- Bleeding
- Increased pain

In the event sedation or dizziness is observed after the procedure, standard of care practices for managing side effects will be performed, and the event will be documented and recorded according to the regulation.

It is understood that there may be as-yet unknown or unanticipated adverse effects of this study treatment. The study team will continually monitor for these effects and consider altering the protocol if needed to ensure patient safety. Changes in the procedures of the study, as well as any change(s) in the risks and/or benefits will be presented to and discussed with the subjects upon approval from the appropriate regulatory bodies for implementation of such revision(s).

Safety Monitoring:

Patients are examined on the day of the procedure to confirm the source of pain, vital signs are stable and in normal range, and female patients are confirmed not-pregnant through point of care pregnancy tests. During the procedure continuous pulse oximetry is used to monitor oxygenation, blood pressure is obtained every 2 minutes, and 3-lead electrocardiogram is monitored for heart rate and rhythm. Following the procedure, patients are taken to the recovery room adjacent to the procedure room to be monitored for 1 hour with continuous pulse oximetry, blood pressure (measured every 5 minutes), and continuous ECG to ensure stable vital signs. The patients are discharged home with a responsible adult after recovery. Before, during, and after the procedure patients are monitored by a registered nurse skilled in the evaluation of vital signs and familiar with the procedure. [name] is an Anesthesiologist and will be present for the duration of patient care.

Data Monitoring:

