The trigeminal block procedure is standard of care in the pain clinic. Expected effects of successful block include transient numbness, transient facial weakness including ipsilateral eyelid lag, and rare visual changes all of which resolve with the resolution of the effects of lidocaine over the typical course of 2 hours. Rare risks of the block procedure include infection, bleeding, nerve injury from the mechanical placement of the block needle. Rare risks of using lidocaine during the block procedure include intravascular or subdural injection resulting in transient unresponsiveness and/or seizure, mild sedation, bradycardia, and arrhythmias. These rare risks and side-effects must be differentiated from potential side-effects due to the addition of guanfacine. As all eligible patients are in

clinic for diagnostic nerve block as standard of care, they will receive clinical consent to treatment for the injection procedure itself and necessary x-ray radiation as part of routine care.

Common side-effects of daily oral use of guanfacine include dizziness, drowsiness, tiredness, low blood pressure, and slow heart rate. These side-effects are similar among other medications in the same class including clonidine, dexmedetomidine, tizanidine. Clonidine is also used as an intrathecal analgesic and as a perineural adjunctive injectate for regional blocks. We would expect that the side-effects of guanfacine as an adjunct to lidocaine block might additionally include increased dizziness, drowsiness, tiredness, low blood pressure, and slow heart rate. If the level of sedation experienced by at least 20% of patients in either group is greater than anticipated either by severity or duration, study enrollment will be stopped and the safety monitor engaged for an interim review of data comparing the study groups. If oversedation is occurring in only one group, an adjustment will be made to maintain monitoring for more than an hour (as is standard) until complete recovery.

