Potential adverse events (AE) including any occurrence of the above listed procedural or medicine-related side-effects and risks will be documented as AE's, described and categorized as mild-, moderate-, severe- AE and submitted for review by the safety monitor and IRB. The PI will also submit the likelihood of the AE being potentially related to the use of guanfacine. Severe AEs would include the occurrence of a seizure, severe sedation requiring ventilation support; bradycardia, unstable arrhythmias, or hypotension requiring resuscitation (medical or mechanical). The occurrence of a severe AE that is deemed study related would result in a stop of enrollment to report the data to the IRB, and FDA guidance would be obtained prior to study restart.

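### The safety endpoint leaves out low blood pressure, slow heart rate and other effects expected of guanfacine, and its standard of comparability has no margin or planned analysis

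*Combined protocol and SAP*

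**What the plan says.** Section 1.0 gives two objectives. The second is "The safety and tolerability of a single dose of guanfacine in combination with lidocaine compared to lidocaine alone". Section 2.0 turns this into a safety endpoint: "comparable side effect profile of combination product compared to lidocaine alone on relevant adverse event measures: sedation, local site reaction, confusion".

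Section 7.0 (Safety Stopping Criteria) states what guanfacine is expected to add to a lidocaine block. The side effects "might additionally include increased dizziness, drowsiness, tiredness, low blood pressure, and slow heart rate". Section 6.0 also lists bradycardia, hypotension and dizziness among the risks.

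The relevant signals are monitored. During the procedure, "blood pressure is obtained every 2 minutes, and 3-lead electrocardiogram is monitored for heart rate and rhythm". For one hour in recovery, monitoring includes "blood pressure (measured every 5 minutes), and continuous ECG to ensure stable vital signs". The Section 5.0 schedule has vital signs at all three visits and continuous ECG at both procedure visits, with neither in the follow-up periods.

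Section 7.0 requires every occurrence of the listed side effects to be documented as an adverse event, graded, and sent to the safety monitor and the IRB. Bradycardia or hypotension needing resuscitation counts as severe, and a severe event judged study-related halts enrollment.

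Section 9.0 sets out models for the primary and secondary outcomes and gives power for the primary outcome only. It names no safety measure, contrast, margin or event rate.

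**The concern.** The endpoint and the protocol's own expectations do not match. Of the five effects listed in Section 7.0, the endpoint covers drowsiness (as sedation) but not dizziness, tiredness, low blood pressure or slow heart rate. It does name confusion, which appears neither in that list nor among the Section 6.0 risks.

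The endpoint is also worded as a result to be shown, a "comparable side effect profile of combination product", with no rule for deciding whether it has been shown. A report that follows the plan as written could therefore state that the safety profile is comparable without having compared two expected haemodynamic effects. For the effects it did compare, it could do so without having excluded a sizeable increase. Safety is one of only two study objectives, so the wording bears directly on what the trial can conclude.

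**Working it through.** **1. The plan's own figure.** Section 9.1 states about 90% power with 30 participants for a 28-minute difference, with between- and within-participant SDs of 30 minutes.
- SD of the within-participant difference = 30 × √2 = 42.43 minutes.
- Noncentrality = 30 × 28² / 42.43² = 30 × 784 / 1800 = 13.07.
- Power of the planned two-degree-of-freedom test at 5% (chi-square form) = 90.9%.

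The figure reproduces. It concerns duration of pain relief only and does not carry over to the safety endpoint.

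**2. Inputs for safety.** From the documents: 30 administrations per treatment, 30 expected completers (Section 9.1) and a 5% type-I error rate, taken as two-sided. Not in the documents and therefore assumed: event rates of 5% to 30%, margins of 10 to 30 points, and independence within participant (correlation 0.3 as a variant).

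**3. Precision with 30 pairs.**
- Half-width of the 95% CI at 10% on both treatments = 1.96 × √(2 × 0.10 × 0.90 / 30) = 15.2 points, or 12.7 points with correlation 0.3.
- The same formula gives 11 points at a 5% rate, 20 at 20% and 23 at 30%.
- Zero events in 30: exact two-sided 95% upper limit = 1 − 0.025^(1/30) = 11.6%.

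**4. Power to detect a real increase** (exact McNemar, 30 pairs, independence): 9.6% for 10% versus 20%, and 35.8% for 10% versus 30%.

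**5. Power to show no more than a given excess** (Tango score test for paired proportions, one-sided 2.5%, equal true rates, 30 pairs; correlation 0.3 in brackets):

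| Assumed rate | 10-point margin | 15-point margin | 20-point margin |
|---|---|---|---|
| 5% | 25% (27%) | 54% (61%) | 79% (86%) |
| 10% | 19% (22%) | 39% (48%) | 63% (72%) |
| 20% | 15% (17%) | 30% (35%) | 48% (58%) |
| 30% | 13% (15%) | 25% (31%) | 39% (51%) |

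Under independence, a 25-point margin gives 84% power at a 10% rate, and a 30-point margin gives 81% at 20%.

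**6. Thirty pairs may be optimistic.** Section 2.0 counts 30 versus 30 administrations from about 40 starters. That count could be met by 20 pairs plus 20 single-period participants, 10 on each treatment (20 + 10 = 30 per treatment). With 20 pairs alone, the McNemar powers in step 4 fall to about 4% and 19%.

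**The case against.** The strongest reply is that safety oversight is in place. A reader might infer that low blood pressure and slow heart rate go unmonitored, or become adverse events only when the investigator thinks a vital-sign change matters. The general adverse-event definition in Section 7.0 has such a clause. However, the Safety Stopping Criteria separately require any occurrence of the listed side effects to be documented, and that list includes both. This part of the reply stands: the gap is in the endpoint and its analysis, not in capture. What remains is that neither effect has a numerical definition.

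A reader might also infer that these two effects are the likeliest to differ between treatments. The documents do not rank the five effects, and they say only that these might occur. Sedation is in the endpoint and is the only effect with a numerical trigger for review (20%).

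Nor do the documents say that a non-significant difference will be read as comparability, since no safety test is planned at all. The problem is that no criterion exists, not that a wrong one has been adopted.

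Finally, this is a pilot with objectives described as exploratory, and low power for adverse events is normal at this size. That is fair, and more participants are not needed. It is a reason to report estimates with intervals rather than a claim of comparability.

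**Conclusion.** The point holds in this form: the treatment comparison in the safety endpoint omits low blood pressure, slow heart rate, dizziness and tiredness, all expected by the protocol, and comparability has neither a margin nor a planned analysis.

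The size of the second part depends on assumed rates and margins. For margins up to 15 points, power stays at or below 61% over assumed rates of 5% to 30%. It reaches about 80% at 20 points only if rates are near 5%; at rates of 10% to 20% it needs roughly 25 to 30 points. It would be too strong to say that 30 pairs could support no margin at all, because a wide one is reachable at low rates. The supported conclusion is that the trial can estimate the safety difference but cannot establish comparability within a narrow margin.

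This should be changed before unblinding. It does not affect the primary analysis.

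**What to change.** **Section 2.0.** Add hypotension and bradycardia, and the other effects expected in Section 7.0, to the safety endpoint. The sponsor sets the definitions before unblinding. Base them on the procedure and one-hour recovery readings together with adverse-event reports. State that the readings must be entered in the study database, because the protocol describes them as monitoring and does not say that each one is recorded there. State also that they cover only that window; Section 1.0 gives guanfacine an elimination half-life of about 17 hours, so later effects would rest on adverse-event reports.

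**Section 9.0.** Report each safety measure by treatment over all administrations received, as a risk difference with a 95% confidence interval that accounts for within-participant correlation and, where estimable, order. Include first-block data from participants who do not have a second block, as Sections 5.0 and 9.1 already require for the analysis. Intolerable toxicity is a stated reason for not receiving both treatments, so an analysis of pairs alone could drop the participants who tolerated treatment worst. Give the paired result in completers as supportive.

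**Wording.** Replace the comparability claim with these estimates.

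**Cost.** Endpoint and analysis wording, some extra data entry and analysis, and a less favourable safety statement. No added participants, visits or monitoring.
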